14.2.7 Time to New Subsequent Systemic Cancer Treatment

[figure not shown]
The time to new subsequent systemic cancer treatment (NAT) (in months) is defined as the time from randomization to first subsequent systemic cancer treatment for this disease (LA-SCCHN).

NAT = (date of new subsequent anticancer treatment - randomization date +1) / 30.4375

Participants without documented new subsequent systemic cancer treatment for this disease will be censored at the date of last known contact with evidence of no new systemic cancer treatment.

The secondary endpoint analysis of time to new subsequent systemic cancer treatment will follow the same methods as described for the primary analysis of EFS in Section 14.1.1. Rates will be estimated at 12, 18, 24, 36, 48, and 60 months post-randomization.

CCI

_		

15 Safety Analyses

All safety analyses will be conducted on the SAF set and data will be presented by actual treatment arm (Xevinapant + CRT vs Placebo + CRT), unless otherwise specified.

15.1 Adverse Events

Please refer to Section 9.1.1 of the protocol for the definition of an AE. All AEs (including Adverse Event of Special Interest (AESIs) during the treatment period) will be collected from the time of ICF signature until the EOT visit. From the EOT visit until the EOS visit, only Serious Adverse Event (SAEs) and late-onset AESIs will be collected. AESI definitions used in corresponding analyses are provided in Section 15.2.3.

A treatment-emergent adverse event (TEAE) is any new sign or symptom, disease, other untoward medical event, or change of an existing condition in a participant that begins during the ontreatment period whether or not considered to be drug-related.

Late-onset adverse events are defined as adverse events with first onset of a not-ongoing AE episode after the on-treatment period, i.e., events that start earliest the day after on-treatment period without an incidence of an AE with the same preferred term in the same subject prior or during on-treatment period whether or not considered to be drug-related.

All AEs recorded during the course of the study will be coded with the last available version of MedDRA and will be graded according to NCI-CTCAE version 5.0, as described in Section 9.16 of the protocol.

A treatment-related AE (TRAE) is a TEAE where the Investigator determined it as having a "reasonable causal relationship" to study intervention (done for each study intervention component (xevinapant/matched placebo, CT or IMRT)).

A dose-modifying TEAE is any event which leads to a dose reduction of any of the study intervention components (xevinapant/matched placebo, CT or IMRT).

Missing AE start dates will be imputed as described in Section 9.12.1. Adverse events for which the start date could not be determined after imputation of missing date are considered to be treatment emergent.

For summaries by relationship, AEs with missing relationship will be counted as "reasonable causal relationship". Adverse events with missing NCI-CTCAE grade will not have NCI-CTCAE grade imputed.

All analyses described will be based on TEAEs if not otherwise specified. The AE listings will include all AEs (whether treatment-emergent or not). Non-TEAEs will be flagged in the listings.

All summaries by SOC and PT will display the number and percentage of participants reporting at least one event together with the corresponding number of events (when applicable) and will be grouped by treatment arm. A participant contributes only once to the count for a given TEAE (SOC or PT). If summarized by worst/maximum NCI-CTCAE grade, a participant contributes only once

for a given TEAE (SOC or PT) at the worst/maximum NCI-CTCAE grade. No number of events will be displayed for tables showing the worst/maximum NCI-CTCAE grades. Tables will be sorted by descending overall incidence in SOC and PT. In case of the same incidence, alphabetical order of SOC and PT will be applied.

All summaries by PT will display the number and percentage of participants reporting at least one event together with the corresponding number of events and will be grouped by treatment arm. A participant contributes only once to the count for a given TEAE.

3-tier Approach to Summarizing and Analyzing AEs

The 3-tier approach for summarizing and analyzing AEs in clinical studies will be followed. AEs in different tiers are analyzed using different types of statistical analyses.

Pre-specified AESIs and events of clinical importance (AECI) during the on-treatment period (see Table 20 in Appendix 5) will be analyzed as part of Tier 1 if they fulfill the Rule-of-4 (\geq 4 participants in any of the treatment arms). Otherwise, such AEs will be included in Tier 3. All of the pre-specified events (AESI or AECI as part of Tier 1/Tier 3) will be included in one table. AEs common enough per Rule-of-4 are presented as part of Tier 1, whereas the 95% CI will be omitted for those belonging to Tier 3.

All TEAEs will be classified as belonging to Tier 2 (\geq 4 participants in any of the treatment arms) or Tier 3 (< 4 participants in any of the treatment arms). Analyses methods are provided based on the Rule-of-4.

The Tier 1 and Tier 2 TEAEs will be assessed with a 95% CI for between-group comparisons. For the difference in incidence proportion (risk difference in percentage points), the CIs will be based on Miettinen & Nurminen method (Miettinen & Nurminen (1985)). The Tier 3 AEs will be assessed via summary statistics and risk differences without any CIs.

While analyses will be done for all Tier 2 TEAEs, only TEAEs with incidence proportion $\geq 10\%$ on at least 1 arm will be presented graphically.

No multiplicity adjustment will be applied for Tier 1 and 2 TEAEs.

15.1.1 All Adverse Events

An overall summary of AEs by treatment arm, will show the number and percentage of participants (and the corresponding number of events, when applicable) who report:

- any TEAE
- any NCI-CTCAE grade ≥ 3 TEAE
- any NCI-CTCAE grade ≥ 4 TEAE
- any TEAE with maximum NCI-CTCAE grade 3 (IDMC only)
- any TEAE with maximum NCI-CTCAE grade 4 (IDMC only)
- any treatment-related TEAE (any study treatment and by study treatment components)

- any treatment-related NCI-CTCAE grade ≥ 3 TEAE (any study treatment and by study treatment components)
- any treatment-related NCI-CTCAE grade ≥ 4 TEAE (any study treatment and by study treatment components)
- any treatment-related TEAE with maximum NCI-CTCAE grade 3 (any study treatment and by study treatment components) (IDMC only)
- any treatment-related TEAE with maximum NCI-CTCAE grade 4 (any study treatment and by study treatment components) (IDMC only)
- any treatment-emergent AESI
- any late-onset AESI
- any NCI-CTCAE grade ≥ 3 late-onset AESI
- any NCI-CTCAE grade ≥ 4 late-onset AESI
- any late-onset AESI with maximum NCI-CTCAE grade 3 (IDMC only)
- any late-onset AESI with maximum NCI-CTCAE grade 4 (IDMC only)
- any treatment-related late-onset AESI (any study treatment and by study treatment components)
- any treatment-related NCI-CTCAE grade ≥ 3 late-onset AESI (any study treatment and by study treatment components)
- any treatment-related NCI-CTCAE grade ≥ 4 late-onset AESI (any study treatment and by study treatment components)
- any treatment-related late-onset AESI with maximum NCI-CTCAE grade 3 (any study treatment and by study treatment components) (IDMC only)
- any treatment-related late-onset AESI with maximum NCI-CTCAE grade 4 (any study treatment and by study treatment components) (IDMC only)
- any serious TEAE
- any treatment-related serious TEAE (any study treatment and by study treatment components)
- any TEAE resulting in dose reduction (any study treatment and by study treatment components)
- any TEAE resulting in temporarily treatment interruption (any study treatment and by study treatment components)
- any TEAE resulting in permanently treatment discontinuation (any study treatment and by study treatment components)
- any TEAE leading to death
- any treatment-related TEAE leading to death (any study treatment and by study treatment components)
- any late-onset AEs (starting more than 30 days after the last dose date).

In addition, the following tables summarizing the frequency of participants with TEAEs by SOC and PT will be produced:

- All TEAEs;
- All TEAEs by worst NCI-CTCAE grade (Any, ≥ 3 , ≥ 4 and 5);
- All TEAEs with maximum NCI-CTCAE grade 3 (IDMC only);
- All TEAEs with maximum NCI-CTCAE grade 4 (IDMC only);

- All treatment-related TEAEs (any study treatment and by study treatment components);
- All treatment-related TEAEs by worst NCI-CTCAE grade (Any, ≥ 3 , ≥ 4 and 5)(any study treatment and by study treatment components);
- All treatment-related TEAEs with maximum NCI-CTCAE grade 3 any study treatment and by study treatment components) (IDMC only);
- All treatment-related TEAEs with maximum NCI-CTCAE grade 4 (any study treatment and by study treatment components) (IDMC only);
- All non-serious TEAEs applying a frequency threshold of 5%;
- All TEAEs resulting in dose reduction (any study treatment and by study treatment components);
- All TEAEs resulting in temporarily treatment discontinuation (any study treatment and by study treatment components);
- All late-onset AEs (starting more than 30 days after the last dose date).

In addition, the following tables and figures summarizing the frequency of participants with TEAEs by PT will be produced:

- TEAEs with at least 10% overall incidence (table and figure);
- Treatment-related TEAEs with at least 10% overall incidence (any study treatment and by study treatment components, table and figure).

Furthermore, the following outputs will be provided for the 3-tier approach:

- Pre-specified Tier 1/3 TEAEs (displayed by term and PT including incidences, risk differences and corresponding 95% CIs for the difference in group incidence proportions, as applicable according to rule-of-4)
- Pre-specified Tier 1/3 TEAEs with NCI-CTCAE grade ≥3 (displayed by term and PT including incidences, risk differences and corresponding 95% CIs for the difference in group incidence proportions, as applicable according to rule-of-4)
- Tier 2/3 TEAEs (displayed by SOC and PT including incidences, risk differences and corresponding 95% CIs for the difference in group incidence proportions, as applicable according to Rule-of-4)
- For Tier 1/2 TEAEs each, a Forest plot displaying incidence rates, differences in incidence rates as well as the 95% CIs for the difference will be provided.

Participant data listings will be provided for all AEs, treatment-related AEs and TEAEs considered as being dose-modifying events. Relationship and action taken to each study treatment (xevinapant/matched placebo, CT or IMRT) will be provided.

15.1.2 Adverse Events Leading to Discontinuation of Study Treatment

The frequency (number and percentage) of participants with each of the following will be presented for TEAEs leading to permanent discontinuation of each study treatment by study treatment arm, SOC and PT:

• All TEAEs resulting in treatment discontinuation (any study treatment and by study treatment components).

A listing of all TEAEs leading to treatment discontinuation will also be provided, including relevant information.

15.2 Deaths, Other Serious Adverse Events, and Other Significant Adverse Events

15.2.1 Deaths

The frequency (number and percentage) of participants with each of the following will be presented by treatment arm:

- *All TEAEs leading to death by SOC and PT (IDMC only);*
- Death (overall and by primary reason);
- Death within the on-treatment period (overall and by primary reason);
- Death within 126 days after first dose of study intervention (overall and by primary reason).

Listings will be provided presenting all deaths occurred in the study.

15.2.2 Serious Adverse Events

The frequency (number and percentage) of participants with each of the following will be presented for serious TEAEs by treatment arm, SOC and PT:

- All serious TEAEs
- All treatment-related serious TEAEs (any study treatment and by study treatment components)
- All serious TEAEs by worst NCI-CTCAE grade (Any, ≥ 3 , ≥ 4 and 5)
- All serious treatment-related TEAEs by worst NCI-CTCAE grade (Any, ≥ 3 , ≥ 4 and 5) (any study treatment and by study treatment components)

[figure not shown]
The listings of SAEs will also be provided with the relevant information.

15.2.3 Other Significant Adverse Events

The analyses for AESIs are defined distinguishing 3 main categories, which are defined in Sections 15.2.3.1, 15.2.3.2, and 15.2.3.3 and rely solely on investigator reported AEs. Those are intended as definition for main analyses of AESIs. The legacy definition of AESIs as provided in Section 15.2.3.4 defines the categories of 'AESIs During the On-Treatment Period' and 'Late-onset AESIs During the Follow-up Period', which are supposed to be used for the purpose of consistency with protocol definition. The outputs for analyses based on legacy definition of AESIs must be separated from the main AESI analysis outputs and clearly labeled as AESI per legacy definition.

15.2.3.1 Treatment-emergent AESIs

Treatment-emergent AESIs are defined as TEAEs (see Section 15.1), which match the criteria in Table 20 (see Appendix 5). The potential tier 1 events are defined as the treatment-emergent AESIs and corresponding displays are specified in Section 15.1.1.

[figure not shown]

15.2.3.4 Legacy Definition of AESIs

All AESIs during the on-treatment period following the criteria as described in Appendix 2 will summarize the number and percentage of participants reporting at least one event together with

the corresponding number of events and will be grouped by treatment arm. The following will be displayed:

- Any AESI during treatment period
- Any AESI fulfilling the Aspartate Aminotransferase (AST)/ Alanine Aminotransferase (ALT) criteria
- Any AESI of Lipase > 5* Upper Limit of Normal (ULN)
- Any AESI of Amylase > 5* ULN
- Any AESI fulfilling the acute renal failure criteria
 - o Any renal failure TEAE
 - o Any renal failure (eGFR, CRCL, creatinine elevations)
- Any AESI fulfilling the QT interval corrected using Fridericia's formula (QTcF) prolongation/other Electrocardiogram (ECG) abnormality criteria

15.3 Clinical Laboratory Evaluation

Clinical laboratory results assessed by central and local laboratory will be graded according to NCI-CTCAE, Version 5.0 (see Appendix 3) and classified as low, normal, and high, or normal/abnormal according to the laboratory normal ranges.

All hematology, blood biochemistry, urinalysis, coagulation, and serology evaluations will be listed per participant for each assessment. Standard International System (SI) units will be used for listing and reporting. For continues laboratory results assessed by the central laboratory, actual value observed and change from baseline summary tables will be provided for each laboratory parameter by visit and treatment arm, together with the maximum on-treatment change. For categorical laboratory results frequency tables showing the number and percentage of participants will be provided for each laboratory parameter by visit and treatment arm.

For statistical and graphical summaries of the safety laboratory tests, values below or above the limit of detection (e.g., '<3' or '>500') are substituted with the lower/upper limit of detection (e.g., '<3' is substituted by 3, '>500' is substituted by 500). In the participant data listings, the values will be shown as collected, e.g., including the < or > sign.

69/104

Abnormalities classified according to NCI-CTCAE will be described using the maximum grade. For those parameters which are graded with two toxicities such as potassium (hypokalemia/hyperkalemia), the toxicities will be summarized separately. Low direction toxicity (e.g., hypokalemia) grades at baseline and post baseline will be set to 0 when the variables are derived for summarizing high direction toxicity (e.g., hyperkalemia), and vice versa.

Shifts from baseline NCI-CTCAE grades to maximum on-treatment NCI-CTCAE grade will be presented by treatment arm for central and local laboratory results. Only scheduled visits will be included in the change from baseline summary table; however, unscheduled visits will be included in maximum post-baseline shift tables, liver function tests summaries, and participant data listings. Abnormal laboratory results will be presented in an additional listing.

In addition, a boxplot will be presented for each laboratory parameter assessed by the central laboratory by treatment arm, showing the distributions of change from baseline at each ontreatment study visit.

An eDISH (evaluation of Drug-Induced Serious Hepatotoxicity) plot showing the log/log display of correlation between on-treatment peak total bilirubin versus ALT/AST, both in multiples of ULN, with horizontal and vertical lines indicating Hy's law thresholds, i.e., ALT/AST = $3 \times \text{ULN}$ and total bilirubin = $2 \times \text{ULN}$ for both treatment arms will be provided for central and local laboratory results.

15.4 Vital Signs

Vital sign measurements will include blood pressure (mmHg), heart rate (bpm), temperature (°C), and respiratory rate (breaths/min). Height will only be measured at screening and weight will be measured as indicated in the schedule of events (Section 1.3 of the protocol). If temperature is collected in °F, values will be converted by using °C= (°F - 32) x 5/9. All vital signs measurements will be listed. Actual value observed and change from baseline summary table will be provided for each vital signs parameter by visit and treatment arm together with the maximum on-treatment increase/decrease. The maximum on-treatment increase/decrease from baseline will be calculated by vital sign measurement (temperature increase, weight increase/decrease, heart rate increase/decrease, systolic blood pressure increase/decrease, diastolic blood pressure increase/decrease and respiratory rate increase/decrease). Only scheduled visits will be included in the change from baseline summary table. All visits will be included in the participant data listing.

15.5 Other Safety or Tolerability Evaluations

15.5.1 ECG

A standard single 12-lead ECG will be recorded according to the schedule shown in Table 8-1 of the protocol. In case of abnormal ECG findings, triplicate ECG readings will be performed. Abnormal ECG results including heart rate (bpm), PR interval (msec), RR interval (msec), QRS duration (msec), QT interval (msec), QTcF interval (msec) and morphology rhythm, and classification of within normal limits, abnormal not clinically significant, and abnormal clinically significant with a description for abnormal findings will be presented in a participant data listing.

Actual value observed and change from baseline summary table will be provided for each ECG parameter by visit, time point and treatment arm together with the maximum on-treatment increase/decrease. The maximum on-treatment increase/decrease from baseline will be calculated by ECG measurement (heart rate increase/decrease, PR interval increase, RR interval increase, QRS duration increase, QT interval increase and QTcF interval increase). In case of triplicate ECG readings, the mean of the triplicate ECG parameter values will be used for calculations. For delta QTcF the 90% 2-sided CI will be additionally included with a flag if upper bound > 10 msec.

Shifts from baseline to worst post-baseline values will be presented for the ECG overall evaluation. Additionally, the number and percentage of participants with noteworthy on-treatment QTcF values (<= 450 msec, >450 to 480 msec, >480 to 500 msec, >500 msec) at each timepoint, the number and percentage of participants with noteworthy on-treatment QTcF changes from baseline (<=30 msec, >30 to 60 msec; >60 msec) will be provided by treatment arm for each post-baseline timepoint. In addition, for each post-baseline timepoint the number and percentage of participants with any QTcF value > 500 msec and QTcF change from baseline > 60 msec during the ontreatment period will be displayed.

A box plot will be presented for each ECG parameter by treatment arm, showing the distributions of change from baseline at each on-treatment study visit and timepoint.

Only scheduled visits will be included in summary tables and figures. All visits will be included in the participant data listing.

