6.5.1. Permitted Concomitant Medications

6.5.1.1. Antiemetics

The specific antiemetic regimen is at the discretion of the Investigator, provided adequate control is achieved. Related information should be reported in the eCRF. For participant receiving cisplatin, antiemetic therapy including dexamethasone (or any other corticosteroid at equivalent dose i.v.), 5-HT₃ serotonin receptor antagonists and neurokinin-1 receptor antagonists can be administered as per 2016 MASCC and ESMO guideline (Roila et al. 2016).

For instance, the Investigator can consider the following regimen:

Day of cisplatin administration (Day 1 of cisplatin = Day 2 of each treatment cycle):

- 5-HT₃ serotonin receptor antagonists i.v., at the appropriate antiemetic dose for highly emetogenic regimens. If ondansetron is used with xevinapant/matched placebo, participant should be monitored closely (see also Section 6.5.2).
- Dexamethasone: 12 mg or any other corticosteroid at an equivalent dose orally (to be taken 30 minutes prior to chemotherapy).
- Aprepitant: oral 125 mg at least 30 minutes prior to infusion.

Day 2-3 after cisplatin administration: Dexamethasone 8 mg + aprepitant 80 mg/day ± 5-HT₃ serotonin receptor antagonist

Day 4 after cisplatin administration: Dexamethasone 8 mg

For participants receiving carboplatin, antiemetic therapy including dexamethasone (or any other corticosteroid at an equivalent dose i.v.) and 5-HT₃ serotonin receptor antagonists may be administered as per 2016 MASCC and ESMO guideline (Roila et al. 2016).

Note: Dose and schedule of dexamethasone coupled with its wide availability in various forms established it as the agent of choice in the 2016 MASCC and ESMO guidelines. If an equivalent dose of corticosteroids is used according to institutional guidelines, the risk of increased toxicity to corticosteroids should be carefully monitored. Elevations of plasma levels may be triggered by xevianapant inhibition of CYP3A4.

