Statistical Methods for Key Safety Analysis	Only descriptive statistics will be provided for safety endpoints. Please refer to Section 10.4.4.
CCI	

Abbreviations: BIRC: Blinded Independent Review Committee; CRT: chemoradiotherapy; EFS: event-free survival; IDMC, Independent Data Monitoring Committee; IMRT, intensity-modulated radiotherapy; LA-SCCHN: locally advanced squamous cell carcinoma of the head and neck; OS: overall survival; PA: primary analysis.

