9.2 Definition of Baseline and Change from Baseline

For efficacy analyses, baseline will be defined as the last non-missing measurement prior to randomization. If no such value is available, the last measurement prior to the first study treatment will be used as the baseline measurement.

For safety analyses, the last non-missing measurement prior to the first study treatment will serve as the baseline measurement.

If an assessment that is planned to be performed before randomization, or study treatment per protocol is performed on the same day as the randomization or start of study treatment, respectively, but the assessment time is not available, it will be assumed that it was performed prior and will be considered for derivation of baseline.

If a scheduled pre-dose measurement actually occurred post-dose, then the corresponding measurement will be analyzed similar to an unscheduled post-dose measurement.

If both central and local labs are collected, the baseline will be derived based only on the central lab collected data.

Absolute and percent changes from baseline are defined as

- absolute change = visit value baseline value
- percent change = 100 * (visit value baseline value) / baseline value

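### The 90% CI and 10 ms QTcF flag in SAP 15.5.1 sit on within-arm change from baseline; adding the xevinapant-minus-placebo difference and flagging that would separate drug from background

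*SAP*

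**What the plan says.** SAP Section 15.5.1 plans an ECG table in these terms: "Actual value observed and change from baseline summary table will be provided for each ECG parameter by visit, time point and treatment arm". The same paragraph then adds the QTcF rule: "For delta QTcF the 90% 2-sided CI will be additionally included with a flag if upper bound > 10 msec". The word delta is not defined there. SAP Section 9.2 defines absolute change as visit value minus baseline value, and on the baseline it says: "For safety analyses, the last non-missing measurement prior to the first study treatment will serve as the baseline measurement".

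The other QTcF displays in Section 15.5.1 are also by arm. The change categories "will be provided by treatment arm for each post-baseline timepoint", and the box plots are drawn per arm. The opening of SAP Section 15 sets the general rule: "All safety analyses will be conducted on the SAF set and data will be presented by actual treatment arm". Protocol Table 10-1 sets the level of inference: "Only descriptive statistics will be provided for safety endpoints".

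Protocol Table 8-1 schedules four ECGs after the first dose: C1D1 at 0.5–2 h and 4–6 h, and C1D8 predose and at 0.5–2 h. The schedule is the same in both arms, and randomization is 1:1.

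**The concern.** The QTcF interval and threshold are the only inferential element visible in the ECG section. On the natural reading they apply to the raw change in each arm. That change is the sum of any xevinapant effect and anything else that moves QTcF between the predose reading on C1D1 and the later readings. Both arms receive the same chemoradiotherapy background, so a shift common to both arms enters the flagged quantity in full.

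At stake is how the flag reads. A shared rise can mark the xevinapant arm when the drug does little or nothing, and a shared fall can leave it unmarked when the drug does prolong QTcF. The trial has what is needed to remove the shared part: a concurrent randomized placebo arm with ECGs at the same times.

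**Working it through.** The plan gives no SD, expected shift or operating characteristic for this flag, so there is no figure to reproduce.

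**Inputs from the documents.** 700 participants randomized 1:1, about 350 per arm (Protocol 10.2.1 and 4.1); two-sided 90% CI and 10 ms threshold (SAP 15.5.1).

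**Assumptions.** SD of QTcF change 15, 20 or 25 ms; all 350 per arm evaluable; normal approximation with z = 1.645; the shared shifts and drug effects used below.

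**Half-widths.**

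- By arm: 1.645 × SD / √350. At SD 20: 1.645 × 20 / 18.71 = 1.76 ms.
- Difference, unadjusted: 1.645 × SD × √(2/350). At SD 20: 2.49 ms. The ratio is √2 = 1.41, so about 40% wider.

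**Observed mean at which the flag appears** (10 minus the half-width).

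| SD (ms) | By-arm half-width | By-arm flag if mean exceeds | Difference half-width | Difference flag if mean exceeds |
|---|---|---|---|---|
| 15 | 1.32 | 8.68 | 1.87 | 8.13 |
| 20 | 1.76 | 8.24 | 2.49 | 7.51 |
| 25 | 2.20 | 7.80 | 3.11 | 6.89 |

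**Probability of a flag.** With m the true mean and se the standard error of the flagged quantity, P = 1 − Φ((10 − 1.645·se − m)/se). For the by-arm rule in the xevinapant arm, m is drug effect plus shared shift. For the difference, m is the drug effect alone.

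| Drug effect | Shared shift | By-arm flag, xevinapant (SD 15 / 20 / 25) | Difference flag (SD 15 / 20 / 25) |
|---|---|---|---|
| 0 | +5 | <0.1% / 0.1% / 1.8% | at most 0.01% |
| 0 | +8 | 20% / 41% / 56% | at most 0.01% |
| 0 | +9 | 65% / 76% / 82% | at most 0.01% |
| 5 | +5 | 95% at each SD | 0.3% / 4.8% / 15.8% |
| 10 | 0 | 95% at each SD | 95% at each SD |
| 10 | −3 | 1.8% / 12% / 27% | 95% at each SD |
| 12 | −5 | 1.8% / 12% / 27% | at least 99.6% |

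With no shared shift the two rules agree in the case shown. They separate only as the shift grows.

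**What the planned table would show.** Take observed means equal to the true ones, SD 20.

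- *Effect 12, shift −5.* Xevinapant +7 (upper bound 8.76, no flag), placebo −5 (upper bound −3.24, no flag). The difference is 12, with 90% CI 9.51 to 14.49.
- *Effect 5, shift +5.* Xevinapant +10 (upper bound 11.76, flagged), placebo +5 (upper bound 6.76, no flag). The difference is 5, with upper bound 7.49. Here only the xevinapant column is marked, although the between-arm difference would not be.

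**The case against.** The case against is substantial, and most of it limits the size of the point.

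- **The flag decides nothing.** A reader might take it for a formal signal rule. The documents do not support that: safety is descriptive, no action or error rate is attached, and the participant-level handling of QTcF prolongation in Protocol 8.3.6 does not depend on this table. This stands.
- **Placebo is in the same table.** With no drug effect, a large shared rise would tend to mark both arms, which points to background. In the masking example the gap between +7 and −5 is there to be seen. A reader could even combine the two half-widths in quadrature to obtain the unadjusted interval. So the information is not lost. What is missing is the printed, baseline-adjusted difference and a flag that refers to it.
- **The shared mechanisms are weakly supported.** A reader might infer that cisplatin and antiemetics contaminate all the ECGs. Cisplatin is first given on C1D2, so it cannot affect the C1D1 readings. C1D8 is six days after that dose, and Protocol Appendix 13.2 places the typical onset of renal toxicity in the second week. The example regimen in Protocol 6.5.1.1 gives 5-HT3 antagonists only around the cisplatin dose. The caution there ("If ondansetron is used with xevinapant/matched placebo, participant should be monitored closely") does not mention QT and points to Section 6.5.2, which is redacted. Exclusion criterion 15 also restricts QT-prolonging medication. The documents therefore establish neither the direction nor the size of any shared shift.
- **A between-arm analysis may exist elsewhere.** A reader might conclude that none is planned. That cannot be established: parts of both documents are redacted, Protocol 10.2.3 refers to exposure/response analyses, and SAP 15.1 gives between-group 95% CIs for Tier 1 and Tier 2 adverse events, which could include QT-related terms. The statement holds only for what is visible in Section 15.5.1.

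None of this alters the fact that the interval and threshold are attached to a quantity that mixes drug and background.

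**Conclusion.** The point holds as a modest one about a descriptive output. The sentence does not say per arm and does not define delta; the within-arm reading comes from the table the sentence belongs to and from SAP 9.2. On that reading, a shared shift moves the flag in either direction.

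Under the assumptions used (350 evaluable per arm, SD 15 to 25 ms), a flag with no drug effect needs a shared rise of roughly 8 to 9 ms; a 5 ms rise alone produces one at most 1.8% of the time. Masking needs a shared fall, and the documents name no cause of one. With fewer evaluable participants all the intervals widen. The documents do not support saying that the flag will mislead in this trial. They do support saying that it is not placed on the effect attributable to xevinapant, and that the data to do so are already being collected.

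**What to change.** In SAP Section 15.5.1:

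1. Define delta QTcF explicitly, stating whether it is within-arm change or the between-arm difference.
2. At each scheduled ECG time after the first dose, add the xevinapant-minus-placebo difference in change from baseline, adjusted for baseline QTcF, with its two-sided 90% CI.
3. Put the 10 ms flag on the upper bound of that difference.
4. Keep the by-arm means and intervals as description.

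The cost is one simple model at each of four ECG times, with no new data and no change to participant management. The interval is wider than the by-arm one: a half-width of about 2.5 ms against 1.8 ms at SD 20 (1.9 against 1.3 at SD 15; 3.1 against 2.2 at SD 25), before any gain from baseline adjustment. The wider interval also means that the flag appears at a somewhat smaller observed mean, 7.5 ms rather than 8.2 ms at SD 20. If a between-arm QTcF analysis already exists in a redacted section, a cross-reference and the definition in item 1 would cover most of this, provided that the flag is moved to it.
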